4. GENERAL STATISTICAL CONSIDERATIONS

This SAP was developed based on International Council on Harmonization (ICH) E3 and E9 Guidelines. This SAP should be read in conjunction with the study protocol and electronic case report forms.

Unless otherwise noted, the summary of continuous variables will include the number of nonmissing observations (n), arithmetic mean, median, standard deviation (SD), minimum, and maximum. Percentages will be calculated using the number of subjects within group and overall as the denominator.

All statistical analyses will be conducted using SAS[®] software (Version 9.4 or higher, SAS Institute Inc., Cary, NC).

4.1. Determination of Sample Size

No formal sample size or power calculations were performed. For this initial study in subjects, it is planned to treat and complete safety and tolerability assessments in approximately16 subjects, which is reasonable to assess the primary and exploratory study endpoints. Since subjects may be replaced if they are withdrawn due to major protocol violations, a maximum of 20 subjects will be randomized in the study. It is expected that this number of subjects will provide guidance for the assessment of tolerability in this population and quantify the extent of abdominal pain relief.

4.2. Methods of Assigning Study Participants to Treatment Groups

Subjects who meet all the entry criteria and are eligible for the study will report to the investigator to be randomized on Day 1. Eligible subjects will be randomly assigned to receive 1 of 2 study treatments, either APD371 100 mg TID or APD371 25 mg TID in a 1:1 ratio. The investigator will randomize up to 20 subjects for entry from a sealed envelope held by the Sponsor clinical trial manager.

If a subject in the APD371 100 mg TID group experiences hypotensive symptoms (SBP <90 or DBP <50 mmHg) during the course of study drug treatment, the investigator can instruct the pharmacy to dispense an APD371 50 mg dose. In this situation all other study medication should be returned to the pharmacy.

The analyses for all safety outcomes will use the Safety population which consists of all randomized subjects who received at least 1 dose of study drug; in addition, if a subject is found to have taken a study therapy for the entire duration of the study different from that to which they was randomized, then the subject is counted in the treatment group of the drug they actually received.

4.3. Randomization and Stratification

Subjects will be randomized after the Investigator has verified that they are eligible per criteria in Section 3.5 and Section 3.6 of the protocol. Subjects will then be enrolled into this study and assigned to APD371 25 mg TID or 100 mg TID according to a randomization schedule. Randomization will be stratified by sex.

Randomization will take place across all study sites using a centralized master list held by the Sponsor clinical trial manger, in consultation with the Medical Monitor. When a site is ready to

Statistical Analysis Plan APD371-004

enroll a subject, they will contact the study manager to get the appropriate dose group assignment and unique subject number. The subject's identification number will be used on all of that subject's electronic case report forms (eCRF). Any subject identification numbers that are assigned will not be reused even if the subject does not receive treatment. All subjects must start treatment within 1 week of randomization.

4.4. Blinding

This is an open-label study. For each dose cohort, the Sponsor, contract research organization (CRO), study safety medical monitors, subjects, and personnel involved with the conduct of the study will be unblinded to the identity of study medication.

4.5. Analysis Populations

The following analysis sets are defined in this study:

- The Randomized population will include all randomized subjects.
- The Efficacy population will include all randomized subjects who received at least 1 dose of study medication and have completed at least 7 days of assessments of APS on treatment up to Wk 4. The analyses of all efficacy variables will use the Efficacy population.
- The Per Protocol population will comprise all members of the Efficacy population without a major protocol violation that could affect the validity of efficacy assessments. The Per Protocol population will be used for the analysis of selected endpoints indicated in Section 8. The Per Protocol population will be identified prior to database lock.
- The Safety population will include all randomized subjects who received at least one dose of study medication. The analyses of all safety variables will use Safety population.

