7.2. Study Treatments

The duration of treatment for each subject will be assessed by descriptively summarizing the number of weeks on drug, both as a continuous and categorical variable (e.g., <1 week). In addition, the average daily dose (mg), total exposure (mg), and total duration of treatment in subject-weeks will be summarized by treatment group and overall.

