7.3. Study Treatment Compliance

Compliance will be assessed using subject data recorded in the drug accountability form of the eCRFs. On each day, a subject should take their assigned treatment. The compliance rate for each subject will be computed as $100\% \times (actual number of tablets taken over the study period)/(designated total number of tablets that should have been taken over the study period). Study period is defined as the number of days that the subject has been in the active treatment phase of the trial. Compliance rates will be summarized for each treatment group and overall.$

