13. TABLES, LISTINGS, AND FIGURES

Tables

- Table 14.1.1. Subject Evaluation Groups (All Subjects)
- Table 14.1.2. Subject Enrollment by Center (Randomized Population)
- Table 14.1.3. Subject Disposition (All Subjects)
- Table 14.1.4. Major Protocol Deviations (Efficacy Population)
- Table 14.1.5.1. Demographics and Baseline Characteristics (Safety Population)
- Table 14.1.5.2. Demographics and Baseline Characteristics (Per Protocol Population)
- Table 14.1.6.1.
 Medical History (Safety Population)
- Table 14.1.6.2. Crohn's Disease Medical History (Safety Population)
- Table 14.1.7. Prior Medication Use (Safety Population)
- Table 14.1.8. Concomitant Medications (Safety Population)
- Table 14.1.9.
 Treatment Exposure (Efficacy Population)
- Table 14.1.10. Treatment Compliance (Efficacy Population)
- Table 14.2.1.1. Abdominal Pain Score at Peak and Trough (Efficacy Population)
- Table 14.2.1.2. Abdominal Pain Score at Peak and Trough (Per Protocol Population)
- Table 14.2.1.3. Abdominal Pain Score at Peak and Evening Trough (Efficacy Population)
- Table 14.2.1.4. Abdominal Pain Score at Peak and Evening Trough (Per Protocol Population)
- Table 14.2.2.1. Average Abdominal Pain Score All Subjects (Efficacy Population)
- Table 14.2.2.2. Average Abdominal Pain Score All Subjects (Per Protocol Population)
- Table 14.2.2.3. Average Abdominal Pain Score All Subjects by Sex (Efficacy Population)
- Table 14.2.3.1.
 Average Abdominal Pain Score by Treatment (Efficacy Population)
- Table 14.2.3.2. Average Abdominal Pain Score by Treatment (Per Protocol Population)
- Table 14.2.4. Summary of Daily Abdominal Pain Scores (Efficacy Population)
- Table 14.2.5. Summary of Average Abdominal Pain Score Analyses (Efficacy Population)
- Table 14.2.6.1. Summary of Proportion of Pain Responders (Efficacy Population)
- Table 14.2.6.2. Summary of Proportion of Pain Responders (Per Protocol Population)
- Table 14.2.6.3. Summary of Proportion of Pain Responders (Observed data) (Efficacy Population)
- Table 14.2.6.4. Summary of Proportion of Pain Responders (Observed data) (Per Protocol Population)
- Table 14.2.7.1.Number of Pain-Free Days per Week by Treatment (Efficacy Population)Table 14.2.7.2.Number of Pain-Free Days per Week, Overall (Efficacy Population)

Table 14.2.8. Use of Pain Rescue Medication (Efficacy Population)

 Table 14.2.10.
 Change from Baseline in C-Reactive Protein by Treatment (Efficacy Population)

 Table 14.2.11.

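### The only exposure summary (SAP Table 14.1.9) is on the Efficacy population, so treated subjects with fewer than 7 on-treatment diary days are left out of it

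*SAP*

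**What the plan says.** SAP Section 13 titles Table 14.1.9 "Treatment Exposure (Efficacy Population") and Table 14.1.10 "Treatment Compliance (Efficacy Population"). No Safety-population version of either is listed.

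Under SAP 4.5 the Efficacy population consists of randomized subjects who took at least one dose and "have completed at least 7 days of assessments of APS on treatment up to Wk 4". The Safety population needs only randomization and one dose. On its use, SAP 4.5 says "The analyses of all safety variables will use Safety population", and SAP 4.2 says the same of safety outcomes.

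The body text names no population for either table. SAP 7.2 reads "The duration of treatment for each subject will be assessed by descriptively summarizing the number of weeks on drug". It asks for that duration in two forms, "both as a continuous and categorical variable (e.g., <1 week"). SAP 7.3 begins "The compliance rate for each subject will be computed as" and divides capsules taken by capsules due over the days the subject was in the active treatment phase. The titles in Section 13 are therefore the only specification.

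The other outputs that describe treated subjects mostly use the Safety population. These include demographics (14.1.5.1), medical history (14.1.6.1 and 14.1.6.2), prior and concomitant medication (14.1.7 and 14.1.8), the adverse event, laboratory, ECG and vital-sign tables, and Listings 16.2.5.1 (on-site dosing) and 16.2.5.2 (drug accountability).

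**The concern.** The primary objective is tolerability and safety over up to 8 weeks. A reader sets the adverse event tables beside the exposure table to see how long the subjects behind those events were on drug. As planned, the two tables can rest on different subjects, and the difference is not random: the diary rule removes the shortest exposures, which bear most on tolerability. The subject disposition table (SAP 5.2) gives reasons for stopping, not time on drug, so it does not fill the gap.

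The choice also works against two of the plan's own intentions. SAP 7.2 offers a category for less than one week as its example, and the diary rule largely empties it. The protocol synopsis, under Data Analyses, says safety and tolerability data will be reported by dose and by duration of treatment, which ties time on drug to the safety report.

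The cohorts are small, so a single omitted subject is visible: 1/8 = 12.5% of a planned cohort. Under protocol 5.14.2, treated subjects who discontinue are not replaced, apart from those withdrawn for non-compliance or a major deviation, who may be.

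**Working it through.** The plan states no figure on this point, so there is nothing to reproduce. The arithmetic below only sizes the effect.

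**Inputs from the documents.** 8 subjects per cohort, about 16 in all and at most 20 (protocol 3.1 and 8.2; SAP 4.1); 56 days of treatment (protocol 6.3); the 7-day diary rule (SAP 4.5).

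**Assumptions.** The number and day of early stops, because the documents give neither; all other subjects complete 8 weeks; duration = days on drug / 7, because the SAP gives no formula.

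**Case A: k subjects per arm of 8 stop on Day d, with d from 1 to 6.** None can have 7 on-treatment diary days, so all k are excluded.

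- All treated: total = (8 - k) × 8 + k × d/7 weeks; mean = total/8.
- Table 14.1.9: total = (8 - k) × 8; mean = 8.0.

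| Stops on Day 3 | Table 14.1.9 | All treated |
|---|---|---|
| k = 1: n | 7 | 8 |
| mean, weeks | 8.0 | (56 + 3/7)/8 = 7.05 |
| minimum, weeks | 8.0 | 3/7 = 0.43 |
| subject-weeks | 56.0 | 56.43 |
| k = 2: n | 6 | 8 |
| mean, weeks | 8.0 | (48 + 6/7)/8 = 6.11 |
| minimum, weeks | 8.0 | 0.43 |
| subject-weeks | 48.0 | 48.86 |

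The mean is overstated by 8/7.05 - 1 = 13% for one stopper and 8/6.11 - 1 = 31% for two. Moving the stop from Day 1 to Day 6 changes the all-treated mean only from 7.02 to 7.11 weeks (k = 1) or from 6.04 to 6.21 (k = 2). Subject-weeks are lower by 0.8% and 1.8%. The median is 8.0 either way.

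In the overall column with 16 treated, the mean is 8.0 against (15 × 8 + 3/7)/16 = 7.53 for one stopper, or (14 × 8 + 6/7)/16 = 7.05 for two. With 10 per arm and Day 3 stops, the arm mean is 8.0 against (9 × 8 + 3/7)/10 = 7.24, or (8 × 8 + 6/7)/10 = 6.49.

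**Case B: one subject completes 8 weeks but has fewer than 7 diary days up to Wk 4.**

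- All treated: n 8, mean 8.0, subject-weeks 8 × 8 = 64.
- Table 14.1.9: n 7, mean 8.0, subject-weeks 7 × 8 = 56, a fall of 8/64 = 12.5%.

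The two cases act on different statistics. Early stoppers affect n, the mean, the minimum and the short-exposure count, with little change in subject-weeks. Poor-diary completers affect n and subject-weeks and leave the mean alone.

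**The less-than-one-week category.** With duration = days on drug / 7, a subject below one week has at most 6 days on drug, so none can enter the table. With duration taken as last dose date minus first dose date, a subject dosed on Days 1 to 7 would show 6/7 = 0.86 weeks and could enter. The category therefore holds few or no subjects, depending on a formula the SAP does not state.

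**Compliance (Table 14.1.10).** The denominator is capsules due while the subject was in active treatment, so stopping early does not in itself lower the rate. The direction of any effect of the exclusion cannot be derived from the documents.

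**The case against.** A reader might infer that the titles break the SAP's own rule that safety analyses use the Safety population. The documents do not support that. SAP 4.5 and 4.2 speak of safety variables and outcomes, SAP 9 lists these as adverse events, laboratory parameters, vital signs and ECG, and exposure sits in Section 7. Nor does the reference to each subject in SAP 7.2 and 7.3 settle the population: SAP 8.1 uses similar words for an efficacy variable. This objection stands, and what remains is a criticism of the choice.

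It is also fair to say that no safety estimate changes. Adverse events are reported as numbers and percentages of subjects on the Safety population, and no exposure-adjusted rate is planned. The omitted subjects remain in the disposition table and in Listings 16.2.5.1 and 16.2.5.2, and with at most 20 randomized subjects a reader could pick out the short exposures by hand. This limits the harm, but a summary table that has to be corrected from listings is not doing its job.

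Finally, compliance on the Efficacy population has a purpose. SAP 5.3 tabulates compliance below 80% as a violation in that population, and the Per Protocol set is drawn from it. A reader might infer that Table 14.1.10 overstates compliance; nothing in the documents shows that. The firm recommendation is therefore confined to Table 14.1.9.

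**Conclusion.** The point holds for Table 14.1.9 as a poor choice of population in a trial whose primary objective is tolerability and safety. Where early stoppers exist, the table overstates mean time on drug, hides the shortest exposure and leaves few or no subjects below one week: 8.0 weeks against 7.05 with one Day 3 stopper in an arm of 8, and against 6.11 with two. Where an excluded subject is a completer with a poor diary, the mean is right but an arm of 8 loses one subject and 12.5% of its subject-weeks.

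These figures rest on assumed numbers and days of early stops, completion by everyone else, and a simple duration formula. If every treated subject has 7 on-treatment diary days up to Wk 4, the two populations coincide and nothing changes. The population titles are certain; whether anyone is affected cannot be told from the documents.

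**What to change.** Produce Table 14.1.9 on the Safety population and say so in one sentence in SAP 7.2, so that exposure and adverse events describe the same subjects. State the duration formula there too, so that the short-exposure category is defined.

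Optionally, add a Safety-population version of Table 14.1.10 and name the populations in SAP 7.3. Keep the Efficacy version, which supports the violation row in SAP 5.3 and the Per Protocol set.

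The cost is a population flag, a title and a sentence or two, plus a line in the summary of changes because the SAP amendment follows database lock. That amendment already adds tables and puts populations in the listing titles, so this is work of the same kind. The protocol and every efficacy analysis stay as they are.

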8.3 Analysis Populations

The Safety Population will include all randomized subjects who received at least 1 dose of study medication.

The PK Completers Population will be defined as all subjects who receive APD371 and have at least 5 of the 9 scheduled PK collections on Wk 0 (Day 1), Wk 0 (Day 2) - 2 or Wk 8 (Day -1) and Wk 8, including the pre-dose sample.

The Efficacy population will include all randomized subjects who received at least 1 dose of study medication and have completed at least one consecutive week of APS up to Week 4.

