4.7.3. Missing Data

As described in Section 8.3, in responder analyses, subjects with missing data will be classified as non-responders. Otherwise, there will be no imputation of missing data.

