8.3. Pain Relief Responders

For each of Wks 1, 2, 4, 6, 8 a subject with a missing AAPS will be coded to non-responder. The number and proportion of responders for Wks 1 to 8 and at EOT will be tabulated by treatment group and overall. The difference in proportions of peak, trough, evening trough, and average daily pain weekly responders between the treatment groups at Wk 8 and EOT will be tested by Fisher's exact test and the p-value presented.

These analyses will be repeated for the Per Protocol population.

The percentage of peak, trough, evening trough, and average daily pain weekly responders will be plotted by treatment and visit for the Efficacy population only.

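### The 7-day diary requirement for the Efficacy population keeps first-week stoppers outside the missing-equals-non-responder rule, and no responder analysis on all treated subjects is planned

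*SAP*

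**What the plan says.** On missing data, SAP 4.7.3 states that "in responder analyses, subjects with missing data will be classified as non-responders". SAP 8.3 applies this to Wks 1, 2, 4, 6 and 8: "a subject with a missing AAPS will be coded to non-responder".

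On who is analysed, SAP 4.5 states: "The analyses of all efficacy variables will use the Efficacy population". To enter that population a randomised subject must have taken at least one dose and must "have completed at least 7 days of assessments of APS on treatment up to Wk 4". Protocol 8.3 words the same condition as subjects who "have completed at least one consecutive week of APS up to Week 4". An all-treated set is defined in SAP 4.5 but assigned to safety variables: "The Safety population will include all randomized subjects who received at least one dose of study medication".

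On the comparison, SAP 8.3 says that the difference in responder proportions "between the treatment groups at Wk 8 and EOT will be tested by Fisher's exact test and the p-value presented".

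SAP 13 lists four responder tables (14.2.6.1 to 14.2.6.4) and two responder figures (14.2.2 and 14.2.3). All use the Efficacy population, except Tables 14.2.6.2 and 14.2.6.4, which use its Per Protocol subset. Tables 14.2.6.3 and 14.2.6.4 and Figure 14.2.3 are observed-data displays, which the Amendment 1 summary of changes shows were added after database lock.

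**The concern.** Counting missing as non-response is meant to stop withdrawals from improving a response rate. Here the population filter acts first. A subject who stops in the first week has too few diary days to enter the Efficacy population, so there is no record for the rule to code. The rule reaches later withdrawals but not the earliest ones.

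The exclusion rests on something that happens after randomisation and may depend on dose. If first-week stopping differs between 25 mg and 100 mg, the two denominators shrink unequally, and part of any difference in response would come from the denominators alone. There is no placebo arm. Both documents (Protocol 8.2, SAP 4.1) expect the trial to help quantify pain relief, so the responder percentages are likely to be read at face value.

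**Working it through.** **Inputs.** Planned size is about 16 subjects, 8 per cohort (Protocol 3.1), with a maximum of 20 (Protocol 8.2, SAP 4.1). Treated subjects who discontinue are not replaced, apart from some withdrawn for non-compliance or a major deviation (Protocol 5.14.2). The documents give no expected response rate, early-withdrawal rate or power, so the plan's only figure to reproduce is 2 × 8 = 16, which agrees. The number of excluded subjects, k, is an assumption and is shown as a range.

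**Order of the rules.** Dose taken → 7 diary days on treatment? → if not, not in the Efficacy population → no responder record → missing-data rule has nothing to act on. SAP 4 takes percentages over the number of subjects in the group, which does not bring the excluded subjects back.

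**Size from Wk 2 on.** Let n be the treated subjects in an arm, k the first-week stoppers with no later AAPS, and r the responders. The planned rate is r/(n−k). The all-treated rate is r/n. The difference is rk/[n(n−k)].

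| n = 8 | r | all treated, r/8 | as planned, r/(8−k) | added points |
|---|---|---|---|---|
| k = 0 | any | r/8 | r/8 | 0 |
| k = 1 | 1 | 12.5% | 14.3% | 1.8 |
| k = 1 | 4 | 50.0% | 57.1% | 7.1 |
| k = 1 | 7 | 87.5% | 100.0% | 12.5 |
| k = 2 | 1 | 12.5% | 16.7% | 4.2 |
| k = 2 | 4 | 50.0% | 66.7% | 16.7 |
| k = 2 | 6 | 75.0% | 100.0% | 25.0 |

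If 20 subjects were split 10 and 10, one exclusion in an arm adds 1.1 to 10.0 points and two add 2.5 to 20.0. Pooled over 16 subjects with 8 responders, one exclusion gives 8/15 = 53.3% and two give 8/14 = 57.1%, against 50.0%.

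**Effect on the Fisher test (two-sided).**
- 6/8 against 2/8: p = 1698/12870 = 0.132. With one exclusion in the first arm, 6/7 against 2/8: p = 261/6435 = 0.041. The difference goes from 50.0 to 60.7 points.
- The p-value can also move the other way. 1/8 against 6/8: p = 464/11440 = 0.041. With two exclusions in the first arm, 1/6 against 6/8: p = 352/3432 = 0.103.

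**How likely at least one exclusion is.** With an assumed risk q per subject, the chance of at least one among 16 is 1 − (1−q)^16: 56% at q = 5%, 81% at 10%, 97% at 20%. These are illustrations, not estimates.

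**Where the direction is not fixed.**
- Wk 1: SAP 3.3.2.1 lets the AAPS rest on fewer than 7 days, so an excluded early stopper can have an observed, even responding, value.
- EOT: an APS is taken at early termination (SAP 3.3.2.1), but SAP 3.3.2.2 and 8.3 do not say whether it counts for EOT response.
- Sparse diaries: a subject who stays on drug but has fewer than 7 diary days by Wk 4 is also excluded. AAPS has no stated minimum number of days, so this subject could have a Wk 8 value and be a responder.

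**The case against.** The strongest reply is that the effect is hypothetical and confined to exploratory results. There is no primary endpoint (SAP 3.3.1), no formal testing strategy (SAP 4.6), and SAP 8 allows inferential procedures to be dropped if numbers are very low. The filter comes from the protocol. SAP 5.1 reports population sizes by group and SAP 5.2 reports discontinuations by reason, so a reader could notice excluded subjects and recompute a Wk 8 rate. This stands as a limit on importance. It does not supply the missing analysis: no planned output gives an all-treated response rate, and SAP 5.1 promises reasons for exclusion only for the Per Protocol population.

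A reader might infer that the excluded subjects are mainly tolerability withdrawals and that the reported rates are inflated. The documents do not support that. They give no number, timing or reason for any withdrawal. The dense active-standing tests on Days 1 and 2 are monitoring, not evidence of stopping. Protocol 4.6.1 describes interruption and restart for blood-pressure and heart-rate events, subjects whose dose changes keep scoring pain (Protocol 5.5.1), and the SAP's 7 days may fall anywhere up to Wk 4. A subject interrupted in week 1 may therefore still qualify.

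A reader might also infer that the observed-data displays replace the planned rule. They do not. They are labelled as observed data and disclosed as post-lock additions, and SAP 8.3 still specifies missing as non-response. What remains is that SAP 8.3 does not mention these displays or state their status.

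**Conclusion.** The gap is in the text: the population definition overrides the missing-data rule for first-week stoppers, and no planned responder output includes them. The consequence is conditional. If an arm of 8 has one such subject with no later AAPS and at least one responder, its rate from Wk 2 on, including Wk 8, is 1.8 to 12.5 points higher than on all treated subjects. With two it is 4.2 to 25.0 points higher. If no one is excluded, the results are identical. No direction can be claimed for Wk 1, for EOT, or for subjects on drug with sparse diaries, because an excluded subject there may have an observed score. Tolerability and safety, the primary objective, are analysed on all treated subjects and are unaffected. The change is worth making because it is cheap and removes an exclusion based on a post-randomisation event.

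**What to change.** - In SAP 8.3, report the weekly and EOT responder proportions and the Fisher tests on all randomised subjects who received at least one dose, counting a missing AAPS as non-response. Show this next to the Efficacy-population version.
- Add a matching exception in SAP 4.5, and record the departure from Protocol 8.3 in SAP 11. Editing 8.3 alone would contradict both population definitions.
- List the subjects excluded from the Efficacy population by arm and reason.
- Label the added analysis as post-lock, and state in 8.3 that the observed-data tables and figure are supportive.
- In the same edit, state whether an early-termination APS counts for EOT, and reconcile 7 days (SAP) with one consecutive week (protocol).

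The cost is SAP wording, one more table and a possibly slightly lower response rate. No new data are needed, and if no one was excluded the added table will show it.
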